13.1.2.2 PFS and OS

Progression-free survival will be measured from study entry to progression or death of any cause, whichever comes first. Overall survival for all will be measured from study entry to death from any cause. Due to small sample size and limit of treatment duration to six months only observed PFS and OS will be reported for patients participating in phase I. For patients who enter on phase II the Kaplan-Meier method will be used to estimate PFS and OS.

14 Procedures and instructions

14.1 Publication of results

Any formal presentation or publication of data from this trial may be published after review and comment by Novartis and Millennium and prior to any outside submission. Novartis and

Millennium must receive copies of any intended communication in advance of publication (at least fifteen working days for presentational materials and abstracts and thirty working days for manuscripts). These requirements acknowledge Novartis' and Millennium's responsibility to provide peer input regarding the scientific content and conclusions of such publications or presentations. Principal Investigation/Institution shall have the final authority to determine the scope and content of its publications, provided such authority shall be exercised with reasonable regard for the interests of Novartis and Millennium and, in accord with the trial contract and shall not permit disclosure of Novartis or Millennium confidential or proprietary information.

14.3 Discontinuation of study

Novartis and Millennium reserve the right to discontinue any study under the conditions specified in the clinical trial agreement.

15 Ethics and Good Clinical Practice

This study must be carried out in compliance with the protocol and the principles of Good Clinical Practice, as described in Novartis and Millennium standard operating procedures and:

1. ICH Harmonized Tripartite Guidelines for Good Clinical Practice 1996. Directive 91/507/EEC, the Rules Governing Medicinal Products in the European Community.
2. US 21 Code of Federal Regulations dealing with clinical studies (including parts 50 and 56 concerning informed consent and IRB regulations).
3. Declaration of Helsinki and amendments, concerning medical research in humans (Recommendations Guiding Physicians in Biomedical Research Involving Human Subjects).

The investigator agrees to adhere to the instructions and procedures described in it and thereby to adhere to the principles of Good Clinical Practice that it conforms to.

15.1 Institutional Review Board/Independent Ethics Committee

Before implementing this study, the protocol, the proposed informed consent form and other information to subjects, must be reviewed by a properly constituted Institutional Review Board/Independent Ethics Committee/Research Ethics Board (IRB/IEC/REB). A signed and dated statement that the protocol and informed consent have been approved by the IRB/IEC/REB must be given to Novartis and Millennium before study initiation. Any

amendments to the protocol, other than administrative ones, must be reviewed by Novartis and Millennium and approved by this committee.

15.2 Informed consent

The investigator must explain to each subject (or legally authorized representative) the nature of the study, its purpose, the procedures involved, the expected duration, the potential risks and benefits involved and any discomfort it may entail. Each subject must be informed that participation in the study is voluntary and that he/she may withdraw from the study at any time and that withdrawal of consent will not affect his/her subsequent medical treatment or relationship with the treating physician.

This informed consent should be given by means of a standard written statement, written in non-technical language. The subject should read and consider the statement before signing and dating it, and should be given a copy of the signed document. If the subject cannot read or sign the documents, oral presentation may be made or signature given by the subject's legally appointed representative, if witnessed by a person not involved in the study, mentioning that the patient could not read or sign the documents. No patient can enter the study before his/her informed consent has been obtained.

The informed consent form is considered to be part of the protocol, and must be submitted by the investigator with it for IRB/IEC/REB approval.

15.3 Investigator and Site Responsibility for Drug Accountability

Accountability for the study drug at all study sites is the responsibility of the principal investigator. The investigator will ensure that the drug is used only in accordance with this protocol. Drug accountability records indicating the drug's delivery date to the site, inventory at the site, use by each patient, and amount returned to Millennium and/or Novartis or a designee or disposal of the drug (if applicable and if approved by Millennium and/or Millennium) will be maintained by the clinical site. Accountability records will include dates, quantities, lot numbers, expiration dates (if applicable), and patient numbers.

15.4 Record Retention

The investigator will maintain all study records according to the ICH-GCP and applicable regulatory and IRB requirement(s).


18 Appendices

19 Medications which have a risk of causing Torsades de pointes ventricular arrhythmia should be avoided

Patients who are currently receiving treatment of the medications in Table 19-1 and cannot either discontinue from this treatment or switch to an alternative medication prior to enrollment in a panobinostat clinical study, will be excluded from the study. Patients may not begin panobinostat treatment with any of the medications listed in Table unless this is discussed with the Sponsor and an approval is granted by the Sponsor. The sponsor may agree to temporarily discontinue panobinostat treatment (e.g., for 72 hours) during administration with these drugs or withheld medications in Table 19-1 for at least 72 hours when panobinostat is to be administered.

NOTE: It is of great importance to avoid combining drugs listed below in Table 19-1 and Table 20-1 (CYP3A inhibitors) especially in the presence of electrolyte abnormalities, notably decreased potassium or magnesium levels commonly associated with diuretic usage.

In generally, medications listed in Table 19-1 should be avoided while medications listed in Tables 20-1 and Table 21-1 are to be used with caution when co-administered with panobinostat. Please select the most stringent recommendation for concomitant medications (i.e., to be avoided) which are common among the tables (e.g., erythromycin, clarithromycin)

Table 19-1 Medications which have a risk of causing Torsades de pointes to be avoided

All Class IA antiarrhythmics
 
 • quinidine • procainamide • disopyramide • any other class IA antiarrhythmic drug

All Class III antiarrhythmics
 
amiodarone
 
sotalol
 
bretylum
 
disopyramide
 
dofetilide
 
ibutilide
 
any other class III antiarrhythmic drug

Antibiotics
 
Macrolide antibiotics*
 
 • erythromycin • clarithromycin • telithromycin 
Quinolone antibiotics*

sparfloxacin
Antipsychotics thioridazine mesoridazine chlorpromazine pimozide
Antimalarials • halofantrine • chloroquine
Miscellaneous drugs • arsenic trioxide • astemizole • bepriidil • domperidone • levomethadyl • methadone • pentamidine • droperidol
*Note: azithromycin, levofloxacin, pefloxacin, ofloxacin, tosufloxacin, difloxacin, temafloxacin, fleroxacin, acrosoxacin, and nalidixic acid are allowed.

This is not a comprehensive list of medications which may prolong the QT interval or have a risk of causing Torsades de pointes. This list of medications was developed in collaboration with an external cardiology consultant, and represents those medications which are deemed to have an unacceptable risk of co-administration with panobinostat.

The following website may be referenced as a supplemental guide for drugs which have been associated with Torsades de pointes or prolonging the QT interval but at this point lack substantial evidence for causing Torsades de pointes:

<http://www.qt drugs.org/medical-pros/drug-lists/drug-lists.htm#>.

Medications listed on the website which do not appear in Table 19-1 above may be used with caution at the discretion of the investigators.

The serotonin (5HT₃) antagonists, often used as antiemetics, such as ondansetron dolasetron, (also are known CYP2D6 substrates, see Table 21-1), or granisetron have been associated with Torsades de points and QT prolongation but have not been shown to cause Torsades de pointes. Therefore, 5HT₃ antagonists are not per se prohibited but close monitoring for signs and symptoms of QT prolongation is recommended. Caution is to be exercised when using these or other agents that may prolong QT intervals in combination with panobinostat.

20 Medications which are known strong CYP3A4/5 inhibitors to be used with caution

Panobinostat is a substrate of CYP3A4 with minor involvement of CYP2D6, and CYP2C19 in *in vitro* evaluation of its metabolism. Thus, a clinical drug-drug interaction study was conducted using ketoconazole, a strong CYP3A inhibitor, in combination with panobinostat in study CLBH589B2110.

Multiple ketoconazole doses at 400 mg increased C_{max} and AUC of panobinostat by 1.6- and 1.8-fold, respectively, but with no change in T_{max} or half-lives in 14 cancer patients. The less than 2-fold increase in panobinostat AUC upon co-administration of a strong CYP3A inhibitor is considered a weak drug inhibition and not clinically relevant, as panobinostat doses at least 2-fold greater than the evaluated 20 mg dose (i.e., 40 mg and 60 mg) have been safely administered in patients. Thus, co-administration of panobinostat with a moderate or weak CYP3A inhibitor is allowed. However, clinical monitoring of signs and symptoms of panobinostat treatment related adverse events is recommended when long-term (≥ 1 week) concomitant administration of any strong CYP3A inhibitors and panobinostat is medically indicated or investigated in a clinical study.

Patients with impaired liver function (as defined by NCI CTEP criteria)¹ are recommended not to receive panobinostat concomitantly with strong CYP3A inhibitors because potential interaction has not been established in this population.

Table 20-1 Medications which are known strong CYP3A4/5 inhibitors to be used with caution

Macrolide antibiotics*
 
 • clarithromycin • telithromycin • troleandomycin • erythromycin

Antifungals (azoles)*
 
 • ketoconazole • itraconazole • fluconazole

Antidepressants
 
 • nefazodone

Calcium channel blockers*
 
 • diltiazem • verapamil

HIV protease inhibitors:
 
 • indinavir • nelfinavir • ritonavir

 • saquinavir
Miscellaneous drugs or products 
 • aprepitant • grapefruit product or juice
* azithromycin, regular orange juice and dihydropyridine calcium channel blockers (e.g. amlodipine, felodipine, nicardipine, nifedipine) are allowed.

This is not a comprehensive list of medications which may inhibit CYP3A4/5. Additional updated versions with moderate and weak CYP3A inhibitors, which are meant to be used as a guide, may be found at the following website: <http://medicine.iupui.edu/clinpharm/DDIs>

21 Medications which are known CYP2D6 substrates to be used with caution

Panobinostat was also shown to be a CYP2D6 inhibitor (K_i 0.17 μM) *in vitro*. Thus, clinical drug-drug interaction study with panobinostat as CYP2D6 inhibitor and dextromethorphan as CYP2D6 substrate was recently conducted in study CLBH589B2109.

Multiple panobinostat doses increased C_{max} and AUC of dextromethorphan by a mean of 1.8- and 1.6-fold respectively, but with no change in T_{max} in 17 cancer patients. An approximately 2-fold increase in dextromethorphan AUC upon co-administration with panobinostat indicated that *in vivo* CYP2D6 inhibition of panobinostat is weak.

As the study was conducted using a sensitive CYP2D6 substrate which resulted in a weak inhibition, drugs with a large therapeutic index such as anti-emetics, anti-hypertensives, and anti-depressants are generally safe to be co-administered with panobinostat.

Patients should be carefully monitored for potential signs and symptoms of toxicity and may require dose titration or dose reduction of a sensitive CYP2D6 substrate which also have a narrow therapeutic window (e.g., the ratio of toxicity exposure is \leq 2-fold higher than the efficacious or therapeutic exposure).

Table 21-1 Medications which are known CYP2D6 substrates to be used with caution

Beta blockers (listed below):	Antipsychotics (listed below):
carvedilol	aripiprazole
metoprolol	haloperidol
propafenone	perphenazine
timolol	risperidone
Antidepressants (listed below):	thioridazine
amitriptyline	zuclopenthixol
chlormipramine	amphetamine

desipramine	alprenolol
imipramine	bufuralol
fluoxetine	chloropheniramine
paroxetine	Antiarrhythmics (listed below):
venlafaxine	quinidine
bupropion	lidocaine
duloxetine	mexiletine
Antiemetics (listed below):	propafenone
dolasetron	Others:
ondansetron	oxycodone
metoclopramide	codeine
	hydrocodone
	terbinafine
	promethazine
	tamoxifen
	tramadol

This is not a comprehensive list of CYP2D6 substrates. Additional updated versions of this list, which are meant to be used as a guide, may be found at the following website: <http://medicine.iupui.edu/clinpharm/DDIs> Synold TW, Takimoto CH, Doroshow JH, Gandara D, Mani S, Remick SC, Mulkerin DL, Hamilton A, Sharma S, Ramanathan RK, Lenz HJ, Graham M, Longmate J, Kaufman BM, Ivy SP. Dose-Escalating and Pharmacological Study of Oxaliplatin in Adult Cancer Patients with Impaired Hepatic Function: A National Cancer Institute Organ Dysfunction Working Group Study, Clin Cancer Res. 2007 13; 3660

22 Cockcroft-Gault estimation of CrCl

Cockcroft-Gault estimation of creatinine clearance (CrCl):

(Cockcroft, 1976; Luke 1990)

$$\text{CrCl (mL/min)} = \frac{(140 - \text{age}) \times (\text{weight, kg})}{72 \times (\text{serum creatinine, mg/dL})}$$

(Males)

Pregnancy Form v03Nov2008 (IIS)

MOTHER'S INFORMATION:	
Initials: _____ Date of Birth:   /   /   or Age: _____ years <small style="margin-left: 100px;">DD MM Yr</small>	
Participating in an MPI clinical study?  No  Yes If no, what company product was taken: _____ If yes, please provide: Study drug: _____ Protocol No: _____ Center No: _____ Patient No: _____	Race: _____ Occupation: _____
Medical / Familial / Social History (i.e. Include alcohol/tobacco and substance abuse; complications of past pregnancy, labor/delivery, fetus/baby; illnesses during this pregnancy; assisted conception: specify; other disorders including familial birth defects/genetic/chromosomal disorders; method of diagnosis consanguinity, etc.) _____ _____ _____	Number of previous pregnancies: Full term _____ Pre-term _____ Outcomes of previous pregnancies: (Please indicate number of occurrences) • Spontaneous abortion: _____ • Normal live birth: _____ • Therapeutic abortion: _____ • Children born with defects: _____ • Elective abortion: _____ • Stillbirth: _____ • Other: _____ • Outcome unknown: _____

MOTHER'S DRUG EXPOSURE INFORMATION						
Please include medical prescriptions, vaccinations, medical devices, OTC products, pregnancy supplements (such as folic acid, multivitamins)						
Product Name	Dosage	Route administered to patient	Date of first use (DD/MM/Yr)	Date of end treatment (DD/MM/Yr)	Indication	Contraindicated to pregnancy
			(/ /)	(/ /)		 Yes  No  Unk
			(/ /)	(/ /)		 Yes  No  Unk
			(/ /)	(/ /)		 Yes  No  Unk
			(/ /)	(/ /)		 Yes  No  Unk

Summary of Changes:

April 24, 2014: Amendment 1

- Cover page: added [name] as UH investigator
- Section 7.6.1: pg. 61 changed CRF to Oncore
- Section 8: pg. 69 -70 changes on the schedule of assessments and foot notes for some additional clarifications
- Pgs. 76-87 administrative changes brought to our attention

May 6, 2014: Amendment 2

- Table 7.5 pg. 57 the parameters for QTCF was changed to ≥ 481 since it would otherwise contradict parameters to start a new cycle (7.4; QTCF ≤ 480 = grade 1).
- Table 8.1 pg. 69 myeloma parameters removed from day 1 cycle one in schedule of assessments (table 8.1) since they are already included in screening (day -7 to 1) and do not need to be repeated for any safety concerns

June 18, 2014: Amendment 3

- Section 10.4 pg. 82 Added: Follow up for detection of second primary malignancies beyond the planned study is not required; however, if the sponsor-investigator learns about the occurrence of a second primary malignancy in one of the study subjects within 3 years after the last study drug administration he must report the event to Millennium Pharmacovigilance (or designee).

December 26, 2014: Amendment 4

Cover: Replaced [name] with [name] as UH PI

- 1. 5.4: Dose Limiting Toxicities: Pg. 42**
 - Use of G-CSF or platelet transfusions in cycle one
 - Neutropenic fever (with grade 3 or grade 4 neutropenia)
- 2. 6.1.2: Inclusion/Exclusion: Pg. 45 and 46**
 - Updated Inclusion Criteria # 12
 - added Inclusion criteria # 13
 - Updated Exclusion Criteria # 1
 - Added # 2
 - Updated #'s 5, 6 and 9
 - deleted Exclusion criteria # 11 (was added to Inclusion)
- 3. 7.1.3: Cardiac Precautions – Pg. 51**

- deleted phosphorus
- 4. 7.4: Instructions for Initiation of a New Cycle: Pg. 52**
 - Platelets $\geq 50 \times 10^9/L$, without platelet transfusion for $\geq 72h$
- 5. 7.5.4: Dose Modifications for Prolonged QTcF: Pg. 58-63**
 - Tables Updated
- 6. 7.6.1: Drug Discontinuation: Pg. 66**
 - Dosing delay of > 21 days (= unable to receive study therapy for 22 days including any therapy held during a cycle)
 - Delay of a cycle by > 14 days from the intended day of the next scheduled dose, counted from the start of the previous cycle.
- 7. 7.7.2: Summary of Prohibited Concomitant Medications and Supplements: Pg. 68**
 - Non-steroidal anti-inflammatory agents (NSAIDs) should be avoided if possible due to risk for kidney dysfunction in myeloma but if clinical judgement strongly argues for their use patients can remain on study while receiving NSAIDs
 - Platelet transfusions can be given as clinically indicated but eligibility for starting a new cycle needs to be determined after at least 72 h without platelet transfusion and eligibility for inclusion in this trial needs to be determined after at least 7 days without platelet transfusion.
- 8. 8.0: Visit Schedule and Assessments: Pg. 73**
 - Added Physical Exam at Screening
 - Deleted Weekly ECGs (typo)
 - Updated ISTAT BMP info.
 - Updated CMP info.
 - Footnote #5 regarding ECGs updated
- 9. 9.1.6: ECG Assessments: Pg. 79**
 - Updated tables for ECG from 3 to 1
- 10. 10.0: Safety Monitoring: Pg. 81-88**
 - Multiple updates for Novartis and Millennium Reporting Requirements

June 3, 2015: Amendment 5

- **Cover:** Replaced [name] with [name] as UH PI

- **Pg. 3 Dose Levels:** Patient may continue on Panobinostat behind cycle 6 if disease is at least stable disease free of charge.
- **Pg. 39 Section 5.2: Study Duration:**
 - If the patient's myeloma is controlled in at least stable disease panobinostat may be continued free of charge to the patient. Follow up after completion of cycle 6 is at the discretion of the treating physician but if panobinostat is continued, monitoring for electrolyte abnormalities, especially potassium and magnesium, at a frequency appropriate for the respective patient, is recommended.
 - This protocol may be amended to include a formal maintenance phase and/or a phase II portion after review of safety and preliminary efficacy data.
- **Pg. 69 Visit Schedule and Assessments**
 - Deleted iSTAT BMP weekly and made CMP weekly instead

September 23, 2015: Amendment 6

- Page 1 Increase # of patients to an additional 20 in the Phase 2
- Section 2 Page 40 Rationale for Phase 2
- Section 6 Page 44 Study Population
- Section 6.1.2 Page 44-46 Inclusion Criteria items 3, 8 and 13
- Section 6.1.2 Page 48 Exclusion Criteria item 21
- Section 8 Page 74-75 Visit schedule and assessments

July 18, 2016: Amendment 7

- **Pg. 43 Inclusion Criteria #13 (Added Dara and Elot)** At least 7 days must have passed since the last treatment with lenalidomide, pomalidomide, thalidomide, proteasome inhibitors, or low dose cyclophosphamide (up to 50mg daily), at least 21 days must have passed since the last treatment with **daratumumab, elotuzumab**, investigational therapy and most conventional chemotherapy including cyclophosphamide above 50mg per dose, bendamustine, doxorubicin, cisplatin, and etoposide; and at least 35 days since the last treatment with melphalan.
- **Pg. 50 Section 7.4 Instructions for Initiation of a New Cycle (these were previously deleted in Amendment 6, however we missed a section)**
 - **Deleted:** total serum calcium [corrected for serum albumin] or ionized calcium \geq LLN
 - **Clarified:** QTcF \leq 480 msec if ECG obtained (mandatory before cycle 2)

March 1, 2017: Amendment 8

- Cover Page: Adding NCT #

- Footer: Updated
- Addendum: Summary of Changes

April 3, 2017

- Cover Page: PI from [name] to [name]
- Footer Updated

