10. Other concurrent severe and/or uncontrolled medical conditions (e.g., uncontrolled diabetes or active or uncontrolled infection) including abnormal laboratory values, that could cause unacceptable safety risks or compromise compliance with the protocol
11. Patients using medications that have a relative risk of prolonging the QT interval or inducing torsade de pointes if treatment cannot be discontinued or switched to a different medication prior to starting study drug. If an alternative medication that does not risk QT prolongation can safely be used in the opinion of the treating physician and the treatment is changed to that medication, the patient may be enrolled.
12. Patients who have not passed the nadir of bone marrow suppression from previous anti-myeloma therapy yet. If in doubt, serial CBCs with differential should be obtained.
13. The corticosteroids prednisone and dexamethasone may be continued until the day before treatment start if all related adverse events are controlled at CTCAE version.4.03 grade \leq 1.
14. Patients who have received radiation therapy to more than half of the pelvis or more than half of the spine within \leq 2 weeks prior to starting study treatment; or who have not yet recovered from side effects of such therapies.
15. Patients who have undergone major surgery \leq 4 weeks prior to starting study drug or who have not recovered from side effects of such therapy
16. Systemic treatment, within 14 days before study enrollment, with strong inhibitors of CYP1A2 (fluvoxamine, enoxacin, ciprofloxacin), strong inhibitors of CYP3A (clarithromycin, telithromycin, itraconazole, voriconazole, ketoconazole, nefazodone, posaconazole) or strong CYP3A inducers (rifampin, rifapentine, rifabutin, carbamazepine, phenytoin, phenobarbital), or use of Ginkgo biloba or St. John's wort.
17. Ongoing or active systemic infection, known human immunodeficiency virus (HIV) positive, known active hepatitis B virus hepatitis, or known active hepatitis C virus hepatitis.
18. Concurrent diagnosis of another malignancy if either systemic treatment or surgery is expected to be required within 2 years from study entry.
19. Known allergy to any of the study medications, their analogues, or excipients in the various formulations of any agent.
20. Patients with any significant history of non-compliance to medical regimens or unwilling or unable to comply with the instructions given to him/her by the study staff.

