21. Infection requiring systemic antibiotic therapy or other serious infection within 14 days before study enrollment unless the patient is felt to have fully recovered and any antibiotics that are continued are either beta lactam antibiotics or are specifically allowed on study according to 7.7.1

22. Participation in other clinical trials, including those with other investigational agents not included in this trial, within 21 days of the start of this trial and throughout the duration of this trial.

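### Section 19 lets the Sponsor approve starting panobinostat on a Table 19-1 torsades-risk drug, against its own first sentence and against exclusion 11, 7.7 and 7.7.2

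*Combined protocol and SAP*

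**What the plan says.** Section 19 has three consecutive sentences on Table 19-1 drugs.

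1. A patient taking one who can neither stop it nor switch before enrollment is excluded.
2. Patients may not begin panobinostat with any of the "medications listed in Table unless this is discussed with the Sponsor and an approval is granted by the Sponsor". The table number is missing after the word Table, but the context makes it Table 19-1.
3. "The sponsor may agree to temporarily discontinue panobinostat treatment (e.g., for 72 hours) during administration with these drugs", or may have the "withheld medications in Table 19-1 for at least 72 hours when panobinostat is to be administered".

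Below the table, Section 19 describes the listed drugs as "those medications which are deemed to have an unacceptable risk of co-administration with panobinostat".

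Elsewhere in the protocol:

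- Exclusion 11 (Section 6.1.2) removes "Patients using medications that have a relative risk of prolonging the QT interval or inducing torsade de pointes if treatment cannot be discontinued" or switched before study drug starts. It readmits a patient only after a change to a safe alternative.
- Section 7.7 says that Section 19 drugs are not to be used.
- Section 7.7.2 lists drugs that are not to be used on study, and refers to Sections 19 to 21 for further information.
- Section 6.1.2 requires every criterion to be met and has the principal investigator review the baseline results before enrollment.
- Section 10.2 states that the principal investigator acts as the sponsor.

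**The concern.** The second sentence of Section 19 can be read at a site as permission to start panobinostat in a patient who is still on a torsades-risk drug. The sentence before it and the eligibility list both say that this patient is excluded. A coordinator who consults the appendix and one who consults Section 6.1.2 could reach opposite decisions on the same patient.

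The exception also has no stated conditions. The separation sentence says only what the sponsor may agree to, so approval is not tied to keeping the drugs apart. The person granting approval can be the person confirming eligibility. What is at stake is patient safety at entry and consistent eligibility decisions. No error rate, sample size or analysis is involved.

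**Working it through.** No formula in the plan bears on this, so the check compares texts, with one drug count and one piece of schedule arithmetic.

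**Drug count.** Entries in Table 19-1: class IA 3 + class III 6 + macrolides 3 + quinolone 1 + antipsychotics 4 + antimalarials 2 + miscellaneous 8 = 27. Disopyramide appears under both antiarrhythmic classes, so 27 − 1 = 26 distinct drugs. Checked one by one against Section 7.7.2, 26 of 26 are named there, treating two spelling variants (bretylium, bepridil) as the same drugs.

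**Rules side by side, for a patient on a listed drug that cannot be stopped or switched.**

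| Place | Outcome | Sponsor exception? |
|---|---|---|
| Section 19, sentence 1 | Excluded | No |
| Section 19, sentence 2 | May begin if approved | Yes |
| Exclusion 11 | Excluded | No |
| Section 7.7 | Drug not to be used | No |
| Section 7.7.2 | Drug not to be used | No |

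**Can other text reconcile them?** Two candidates do not.

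- The pointer in 7.7.2 to Sections 19 to 21 is for information and grants nothing. Where 7.7.2 intends an exception, for NSAIDs, it writes it out.
- Section 19 tells the reader to apply the most stringent recommendation, but only for drugs that appear in more than one of its tables. It does not rank the exception against exclusion 11.

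**Schedule.** Section 5.3 gives panobinostat on days 1, 3, 5, 15, 17 and 19 of 28. The gaps between doses are 48, 48, 240, 48, 48 and 240 hours.

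- A 72-hour hold that overlaps a dosing week covers 1 or 2 of the 6 doses, because doses there are 48 hours apart and the week spans 96 hours from first to last dose.
- Inside a 240-hour gap, a 72-hour margin on one side leaves 240 − 72 = 168 hours (7 days) for the listed drug. A margin on both sides leaves 240 − 144 = 96 hours (4 days). In either case no panobinostat dose is lost.

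**The case against.** The best defence reads the second and third sentences together. Both arrangements in the third sentence separate the drugs in time, and temporarily stopping panobinostat presupposes a patient already on it. On that reading Section 19 excludes at entry and, if a listed drug is needed later, asks for consultation and separation. This is a fair account of the third sentence and a reason to keep it: no other section tells the site to hold panobinostat when a listed drug is given on study. It does not rescue the second sentence, which is about beginning treatment and does not make approval depend on separation.

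Existing safeguards also count. A screening QTcF above 470 msec excludes. Potassium, magnesium and calcium must be at or above the lower limit of normal before the first panobinostat dose. ECGs are required before and after dosing on days 1 and 5 of cycle 1. Table 7-5 requires review of concomitant drugs when QTcF is prolonged. These limit harm but do not settle which entry rule applies.

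Several stronger readings are tempting and are not supported:

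- **That 72-hour separation cannot fit the schedule.** The 240-hour gaps allow a course of 4 to 7 days without a missed dose.
- **That four other places bar every listed drug.** Outside Section 19 there are three that cover the whole table: exclusion 11, 7.7 and 7.7.2.
- **That exclusions 16 and 21 add to the contradiction.** Exclusion 16 ("Systemic treatment, within 14 days before study enrollment, with strong inhibitors of CYP1A2 (fluvoxamine, enoxacin, ciprofloxacin), strong inhibitors of CYP3A (clarithromycin, telithromycin" and others) reaches 2 of the 26 drugs and sets a washout before enrollment. That is a different rule from separating doses on study, so its 14 days should not be set against 72 hours. Exclusion 21 requires that "any antibiotics that are continued are either beta lactam antibiotics or are specifically allowed on study according to 7.7.1", but applies only after an infection within 14 days before enrollment. Both operate regardless of Section 19.
- **That the approver is undefined.** Section 10.2 says who acts as sponsor. The protocol summary's mention of a sponsor institution concerns approval of amendments.

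**Conclusion.** The contradiction is real and affects entry decisions. Section 19's second sentence opens a route that its own first sentence, exclusion 11, 7.7 and 7.7.2 close, for all 26 listed drugs, and the approver may be the person who reviews eligibility.

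Severity is minor. The documents give no count of patients on listed drugs, and no effect on an event rate or endpoint is claimed. The conclusion assumes that the incomplete table reference means Table 19-1 and that Sponsor in Section 19 has the meaning given in Section 10.2. The textual conflict does not depend on the second assumption.

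A reader might also infer that Section 19 narrows exclusion 11 to the table's drugs. It does not: it says "This is not a comprehensive list of medications which may prolong the QT interval", and exclusion 11 keeps its wider scope.

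**What to change.** 1. In the second sentence of Section 19, delete everything from the word unless onward and supply the table number. A Table 19-1 drug that cannot be stopped or switched before study drug then always excludes, in line with exclusion 11.
2. Rewrite the third sentence as an on-study rule only: if a listed drug becomes medically unavoidable, panobinostat must be held while it is given and for at least 72 hours after the last dose. Refer to this rule from 7.7 and 7.7.2, so that it does not become a new unannounced exception.

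The 72 hours is Section 19's own figure. The documents give no elimination data for the listed drugs, so it should be stated as a minimum.

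The cost is amendment wording, with no new visits or data. A rare patient who needs a listed drug cannot enter, which exclusion 11 already requires. A patient on study may miss panobinostat doses: none if a course of up to 168 hours falls in a 240-hour gap, and at least 1 or 2 of the 6 in a cycle if the 72-hour hold overlaps a dosing week. A delay of more than 14 days would meet the discontinuation limit in Section 7.6.2.
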